5.2.2 Exclusion Criteria

A subject will not be eligible for study participation if he/she meets any of the following criteria:

1. Male or female subject weighing less than 44 kg (97 lbs.) at screening will be excluded.
2. Mini-Mental State Examination (MMSE) score less than 15 at screening, or cognitive impairment that in the Investigator's opinion would preclude collection of outcome measures. In Germany, for all subjects with an MMSE score of 24 or less

at the time of study entry, an evaluation by an independent psychiatrist will also be requested. If, in the opinion of the independent psychiatrist, subject is unable to provide consent independently, the subject will not be enrolled in the study.

3. Any contraindication or inability to tolerate brain MRIs (e.g., a pacemaker or any other implanted device or condition that would preclude proximity to a strong magnetic field).
4. During enrollment of Cohort 1 and Cohort J1, any contraindication or inability to tolerate lumbar punctures (LP) (e.g., use of anticoagulant medications such as warfarin) are exclusionary. During enrollment of Cohort 2, subjects who are not able to undergo LP may be admitted with permission of the AbbVie Medical Director, and these subjects will not be required to undergo LP during the study.
5. Subject resides at a skilled nursing or dementia care facility, or admission to such a facility is planned during the study period.
6. Evidence of any neurological disorder that could explain signs of PSP, including:
 - a. Signs of idiopathic Parkinson's disease (e.g., severe asymmetric parkinsonian signs, clinically significant tremor at rest, or prominent and sustained response to levodopa therapy)
 - b. Signs of multiple system atrophy (MSA) (e.g., prominent early cerebellar limb ataxia or unexplained symptomatic autonomic dysfunction)
 - c. Signs of Lewy body disease (e.g., hallucinations or delusions unrelated to dopaminergic therapy or other illness)
 - d. Probable Alzheimer's disease according to National Institute of Neurological and Communicative Disorders and Stroke and the Alzheimer's Disease and Related Disorders Association (NINCDS-ADRDA) criteria
 - e. History of repeated strokes with stepwise progression of parkinsonian features
 - f. History of major stroke
 - g. History of severe or repeated head injury
 - h. History of encephalitis

- i. History of neuroleptic use (with the exception of clozapine or quetiapine) for a prolonged period of time or within the past 6 months
 - j. Oculogyric crises
 - k. Street-drug-related parkinsonism
 - l. Known history of autosomal dominant PSP due to a microtubule associated protein tau (*MAPT*) mutation
 - m. Known history of an autosomal dominant mutation associated with frontotemporal lobar degeneration (FTLD) (e.g., an autosomal dominant mutation in *C90RF72* or *GRN*)
 - n. Significant other neurological disease on MRI that could account for PSP symptoms
7. Evidence of any clinically significant neurological disorder other than PSP, including but not limited to significant cerebrovascular abnormalities, vascular dementia, motor neuron disease or amyotrophic lateral sclerosis (ALS), Huntington's disease, normal pressure hydrocephalus, brain tumor, seizure disorder, multiple sclerosis, or known structural brain abnormalities.
 8. The subject has a history of or currently has schizophrenia, schizoaffective disorder or bipolar disorder according to Diagnostic and Statistical Manual of Mental Disorders, 5th Edition (DSM-V) or International Classification of Diseases (ICD)-10 criteria.
 9. In the opinion of the investigator, the subject has any clinically significant uncontrolled psychiatric illness.
 10. Subject has significant current suicidal ideation within one year prior to screening as evidenced by answering "yes" to questions 4 or 5 on the suicidal ideation portion of the Columbia-Suicide Severity Rating Scale (C-SSRS) completed at screening or a history of suicidal attempts within the last 2 years.
 11. Positive screen for drugs of abuse or marijuana at screening visit.

12. Current diagnosis or history of drug or alcohol abuse (by DSM-V criteria) within 24 months prior to screening visit.
13. Subject has had a significant illness or infection requiring medical intervention in the past 30 days.
14. Subject has a positive test result for hepatitis B surface antigen (HbsAg) or hepatitis C virus antibody (HCV Ab), or a known history of Human Immunodeficiency Virus (HIV) infection.
15. The subject has a history or evidence of a malignancy within the 2 years prior to the screening visit. Subjects with some indolent malignancies (e.g., basal cell carcinoma or squamous cell carcinoma of the skin) may be permitted to enroll with the permission of the AbbVie Medical Director.
16. Subject has had a myocardial infarction, advanced chronic heart failure, unstable angina, stroke, transient ischemic attack (TIA), clinically significant conduction abnormalities, or required intervention for any of these conditions (e.g., coronary artery bypass graft, percutaneous coronary intervention via cardiac catheterization, or thrombolytic therapy), within 1 year of screening.
17. Any clinically significant hematological, autoimmune, endocrine, cardiovascular, neoplastic, renal, gastrointestinal, or other disorder that, in the Investigator's opinion, could interfere with the subject's participation in the study, place the subject at increased risk, or confound interpretation of study results.
18. Subject has a planned major surgical procedure scheduled during the period when the subject would be participating in this study. The subject may subsequently be considered for the study following full recuperation from the surgical procedure.
19. History of serious adverse reaction to ABBV-8E12 or other monoclonal antibodies or biologics.
20. Subject has received an investigational product (other than ABBV-8E12, also known as C₂N 8E12) within a time period equal to 5 half-lives, if known, or within

6 weeks (for small molecules) or 6 months (for monoclonal antibodies or other biologics) prior to study drug administration.

21. Subject is using any exclusionary medications as defined in Section 5.2.3.1.
22. Subject has any history of prior receipt of active immunotherapy directed against tau.
23. Current enrollment in another interventional clinical study involving a therapeutic agent.
24. Male subject who is considering fathering a child or donating sperm during the study or for approximately 20 weeks after the last dose of study drug.
25. Subject considered by the investigator, for any reason, an unsuitable candidate to receive ABBV-8E12 or unable or unlikely to comply with the dosing schedule or study evaluations.

Rationale for Exclusion Criteria

- | | |
|-------------------------|---|
| 1, 2, 5 –
17, 22, 25 | These criteria were selected to ensure the appropriate subject population |
| 3, 4, 18, 23 | To ensure the safety of the subjects |
| 19 – 21 | These products may interfere with the pharmacokinetics of the study drug |
| 24 | The effects of ABBV-8E12 on pregnancy are currently unknown |

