No subject experienced a systemic hypersensitivity reaction or injection site reaction, and there have been no clinically relevant patterns of adverse events (AEs) or abnormal laboratory findings observed. Based on available anti-drug antibody (ADA) data in Study C₂N-8E12-WW-104, no ADAs have been detected in post-dose samples on Day 14 and Day 28.

The plasma pharmacokinetic data from Study C₂N-8E12-WW-104 indicate dose-proportional increases in area under the concentration time curve (AUC) from 2.5 to 50 mg/kg. The mean time to maximum plasma concentration (T_{max}) ranged from 0.3 hours to 4.6 hours, and half-life ranged from 27 to 37 days.

Cerebrospinal fluid (CSF) concentrations increased with dose, and the CSF/plasma ABBV-8E12 ratio ranged from 0.181% to 0.385%.

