3.2 Benefits and Risks

ABBV-8E12 was administered under protocol C₂N-8E12-WW-104 to 23 subjects with PSP in single doses up to 50 mg/kg with no clinically concerning safety findings.

In addition, 2 subjects received multiple doses of ABBV-8E12, one under an Expanded Access IND, protocol C₂N-8E12-EA-001 (US) and the other under a single named trial application, C₂N-8E12-DE-003 (Germany). Treatment appeared well tolerated. One subject received 20 monthly doses up to 25 mg/kg and one subject received 3 monthly doses up to 15 mg/kg.

ABBV-8E12 recognizes human tau and does not bind to tau from other species. Off-target toxicity of ABBV-8E12, up to 250 mg/kg/week, was assessed in a 4-week mouse toxicity study. No adverse effects at any dose level were detected. Evidence of efficacy demonstrated in preclinical studies and safety data from clinical studies obtained to date provide a strong rationale for continuing assessment of safety and efficacy in the current study.

The benefit-risk profile will be further defined in this trial.

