***Cohort 2 Allowable PK Windows**

On Days 1, 15, 29, and 85 and at Weeks 24 and 36, the PK samples collected prior to infusion should be collected within 30 minutes of the start of infusion. For 1-hour post-dose sample (Day 15), the allowable PK window is ± 6 minutes, and for 2-hour post-dose samples (Day 15), the allowable PK window is ± 12 minutes. For the samples scheduled for Weeks 52, 60, and 68, the allowable window is ± 4 days.

Blood Samples for ABBV-8E12 Anti-Drug Antibodies (ADA) Assays

Blood samples, approximately 3 mL for ABBV-8E12 ADA analysis will be collected by venipuncture. The collection schedule for ADA will be the same for subjects who previously did or did not participate in the Single-Ascending Dose Study (Study C₂N-8E12-WW-104). The schedule for ABBV-8E12 ADA collection is as follows:

For Subjects Enrolled in Cohort 1 and Cohort J1 (*See Below for Allowable ADA Windows)

- **Days 1, 15, 29, 57, 85, and Weeks 16, 24, and 36 (Doses 1, 2, 3, 4, 5, 6, 8, and 11, respectively)**
 - Prior to the start of the infusion (0 hour, no more than 30 minutes prior to the start of the infusion).
- **Days 89 and 99**
 - Sample may be collected anytime during the day.
- **Week 52: (Study Completion/Premature Discontinuation Visit)**
 - Sample may be collected anytime during the day.
- **Weeks 60 and 68: Post-Treatment Follow-up Period**

- Sample may be collected anytime during the day.

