For the first dose interval, the concentration at the beginning of infusion of the dose will be assumed to be 0 even if the scheduled pre-dose blood sample is mistakenly obtained after the beginning of infusion. For the fifth dose interval, the concentration of the pre-dose sample will be used as the concentration at the beginning of infusion of the dose provided that the blood sample is obtained in the 30 minute interval before the beginning of infusion. If the blood sample is obtained earlier than 30 minutes before the beginning of infusion, for the calculation of AUC the concentration at the beginning of infusion will be the $C_{obs} \times e^{-\beta t}$, where C_{obs} is the reported measurement for the pre-dose concentration, β is the rate constant determined from the exponential curve defined by the last two concentrations in the fifth dose interval and t the length of the time interval between the pre-dose blood sample and the beginning of infusion. If the pre-dose sample for the fifth dose interval is mistakenly obtained after the beginning of infusion of the dose, a value for the concentration at the beginning of the dose interval (beginning of infusion) must be imputed unless the sample was obtained within a very few minutes of the beginning of infusion (< 15 minutes). The data of other subjects in the same treatment group who have values for the concentrations at the beginning of the fifth dose interval, the beginning of the fourth dose interval and the end of the fifth dose interval may be used to obtain a linear regression model for the concentration at the beginning of the fifth dose

interval, with the concentrations at the beginning of the fourth dose interval and the end of the fifth dose interval as explanatory (predictor) variables. The missing value may be replaced by the predicted value from the regression model.

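### The SAP makes no use of the Day 1 pre-dose sample to detect or correct residual ABBV-8E12 in previously exposed subjects, so carried-over drug would count as first-dose exposure

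*Protocol*

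**What the plan says.** **Eligibility.** Protocol 5.2.2 criterion 20 requires 5 half-lives off a prior product if the half-life is known, or else 6 weeks (small molecules) or 6 months (biologics). It applies where a "Subject has received an investigational product (other than ABBV-8E12, also known as" C₂N-8E12). The rationale listed for criteria 19–21 is "These products may interfere with the pharmacokinetics of the study drug". No other criterion sets an interval since the last ABBV-8E12 dose. Criterion 22 concerns active immunotherapy, and criterion 23 bars only "Current enrollment in another interventional clinical study involving a therapeutic agent".

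**Prior exposure is foreseen.** Protocol 5.3.2.1 states: "The collection schedule for ADA will be the same for subjects who previously did or did not participate in the Single-Ascending Dose Study". Protocol 3.2 reports that ABBV-8E12 was given "to 23 subjects with PSP in single doses up to 50 mg/kg", and that 2 further subjects had multiple doses. Protocol 3.0 says that "half-life ranged from 27 to 37 days".

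**What is collected.** A Day 1 pre-infusion serum PK sample is scheduled in every cohort (Protocol 5.3.2.1). Biologics given in the 6 months before study drug are recorded (Protocol 5.3.1.1, Medical History).

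**What the SAP does.** SAP 12.1: "For the first dose interval, the concentration at the beginning of infusion of the dose will be assumed to be 0". For the fifth dose interval the same section uses the measured pre-dose concentration. First-dose Cmax and AUC are derived only in Cohorts 1 and J1 (SAP 4.7). SAP 13.0 uses the last pre-dose total or free tau value as the ANCOVA covariate. Sections 7.2, 10.4, 10.5, 10.7, 12 and 13 contain no flag, covariate, exclusion or sensitivity analysis for prior ABBV-8E12.

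**The concern.** The reason given for criterion 20 is interference with study-drug PK, and residual study drug is the most direct form of that. If a subject starts with drug on board, every post-dose concentration in the first interval is the sum of old and new drug, and the plan attributes all of it to the new dose. The proportional excess is twice as large at 2000 mg as at 4000 mg, so in the dose-normalised analysis it would look like less-than-proportional exposure. The same data set serves the Japan–US exposure comparison in SAP 12.3.

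The tau analysis is exposed too. Protocol 5.6.4 predicts that roughly 75–95% of CSF tau is bound at the study doses and treats free CSF tau as a possible marker of target engagement. The CSF baseline is drawn 8 to 56 days before Day 1, when any residual drug is higher than on Day 1. A free-tau value lowered by old drug would then serve as the covariate.

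Finally, a previously exposed subject randomised to placebo is not drug-naive.

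**Working it through.** **Inputs.** Half-life T = 27 to 37 days (Protocol 3.0). Prior single doses 2.5 to 50 mg/kg and mean weight 74.8 kg (Protocol 5.6.4), taken as 75 kg, giving 187.5 to 3750 mg. Study doses 2000 and 4000 mg. Gap since the last dose: not stated, with 60 days assumed for illustration. Kinetics: mono-exponential decline (assumed).

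**1. Residual at entry.** Fraction left = 2^(−days/T).

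| Days since dose | T = 27 | T = 37 |
|---|---|---|
| 28 | 49% | 59% |
| 60 | 21% | 33% |
| 84 | 12% | 21% |
| 140 | 3% | 7% |
| 182 | 1% | 3% |

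Five half-lives would be 135 to 185 days.

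**2. First-interval AUC excess** = prior dose × fraction left ÷ study dose, at 60 days.

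- 50 mg/kg, 2000 mg arm: 3750 × 0.214 / 2000 = 40%, to 3750 × 0.325 / 2000 = 61%.
- 50 mg/kg, 4000 mg arm: half of that, 20–30%.
- 2.5 mg/kg, 2000 mg arm: 187.5 × 0.214 / 2000 = 2%, to 187.5 × 0.325 / 2000 = 3%.

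Cohorts 1 and J1 hold 39 subjects, so about 39 × 2/3 = 26 on active drug, 13 per arm if allocation is even. One subject with an excess of 40–61% moves an arm's geometric mean by ln(1.40)/13 to ln(1.61)/13, about 2.6–3.7%.

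**3. What the zero rule itself contributes.** It changes only the triangle under the infusion. With an assumed 500 mL volume at 282 mL/hr, the infusion lasts 1.77 h. For a first-dose peak of 1 and T = 27 days, first-interval AUC is about 282 hours × peak. With a residual of half that peak, the area removed is 0.5 × 1.77 × 0.5 = 0.44, and 0.44/282 = 0.16%. With a residual of 5% of the peak it is 0.02%. Cmax is not changed by the rule, because it is taken after infusion starts.

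**4. Day 85 interval.** A dose given 60 days before Day 1 is 60 + 84 = 144 days old by then, leaving 2^(−144/27) = 2.5% to 2^(−144/37) = 6.7%. Study doses on Days 1, 15, 29, 57 and 85 have ages 84, 70, 56, 28 and 0 days, and their remaining fractions sum to 2.01 (T = 27) or 2.42 (T = 37). The excess after 50 mg/kg in the 2000 mg arm is 3750 × 0.0248 / (2000 × 2.01) = 2.3%, to 3750 × 0.0674 / (2000 × 2.42) = 5.2%.

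**5. Primary contrast.** The plan's own figure first: SAP 4.3 gives about 90% power at effect size 0.56 with 25% missing and Bonferroni. With n = 110 × 0.75 = 82.5 per arm and two-sided α = 0.025, power = Φ(0.56/√(2/82.5) − 2.241) = Φ(3.597 − 2.241) = 91.2%, which agrees.

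Now suppose all 23 + 2 = 25 known recipients enrolled (upper bound). That is 25/330 = 7.6%, or about 8.3 of 110 on placebo.

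- Each keeps 1/14 of the 14-dose benefit (assumption): effect 0.56 × (1 − 0.0758/14) = 0.557, power 90.9%.
- Each keeps the full benefit (extreme bound): effect 0.56 × (1 − 0.0758) = 0.518, power 86.1%.

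**The case against.** The case against is strong on several points, and most of it stands.

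- **The zero rule is not the mechanism.** A reader might infer that assuming 0 creates or hides the bias. Step 3 shows that it does not: the excess sits in the post-dose samples whatever starting value is used. Replacing 0 by the measured value, and doing nothing else, would raise AUC slightly.
- **The data are unused, not unseen.** Day 1 pre-dose samples exist in all cohorts, and the 6-month record of biologics (about 182 days) nearly covers five half-lives. SAP 7.3 also summarises previous medications.
- **The upper figure is a stacked case.** It pairs the top prior dose with a gap that no document states. Protocol 5.6.4 calls the single-dose study ongoing in places but also says that it has been completed, and criterion 23 excludes anyone still enrolled in another interventional study.
- **The first interval is the lesser analysis.** Both documents put the greater emphasis on the interval starting at Day 85.
- **Exempting ABBV-8E12 is explicit**, so it may be deliberate in a rare disease with few candidates. That is fair. But the listed PK rationale does not say why it does not extend to the study drug.

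What survives: the plan admits previously exposed subjects, collects the data that would identify many of them, and has no rule that uses those data.

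**Conclusion.** The point holds as a gap in how the SAP handles prior exposure. Some subjects may have residual drug on Day 1. If so, their first-interval Cmax and AUC would be too high, by an amount that runs from negligible to large: at 2000 mg, about 2–3% to 40–61% under the assumed 60-day gap. The set has only about 26 active subjects, so a few could matter. The Day 85 analysis would move far less, about 2–5% in the affected subject even after the top prior dose. The tau baseline could also be affected, by an amount that the documents do not allow one to compute.

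A reader might go further and conclude that residual drug has entered the placebo arm or weakened the primary comparison. The documents do not support that. They state neither the number of previously exposed subjects enrolled nor the time since their last dose, and even if all 25 enrolled, power would go from 91.2% to 90.9% under the one-dose assumption. Only the extreme full-benefit bound gives 86.1%.

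The results rest on mono-exponential decline, a 75 kg subject, and the assumed gap and infusion volume.

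**What to change.** **SAP 12.1.** Limit the assumed 0 to subjects without a quantifiable Day 1 pre-dose concentration. Where it is quantifiable, use the measured value and subtract its exponential decay from first-interval Cmax and AUC, or drop the subject from the first-interval dose-proportionality and regional analyses.

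**SAP 13.0.** Flag subjects with prior ABBV-8E12 exposure, from the recorded history or a quantifiable Day 1 sample, and repeat the CSF and plasma tau ANCOVA without them. The history matters here because the CSF baseline precedes Day 1.

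**SAP 10.4 (optional).** Add one unconditional repeat of the primary MMRM without previously exposed subjects. Section 10.5.1 is the wrong place: it runs only if at least one dose is significant, whereas dilution through the placebo arm would matter most in a null result.

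**Protocol 5.2.2.** Reconcile the ABBV-8E12 exemption in criterion 20 with its stated PK rationale. No particular interval is proposed here.

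**Cost.** SAP wording, one flag from data already collected, and one or two extra model runs. The downside is that a few subjects may leave the first-dose PK set. If no previously exposed subject enrolled, the check documents that.

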5.2.3 Prior and Concomitant Therapy

If a subject reports taking any over-the-counter or prescription medications, vitamins and/or herbal supplements, or if administration of any medication becomes necessary from 30 days prior to screening through the end of the study, the name of the medication, dosage information including dose, route and frequency, date(s) of administration including start and end dates, and reason for use must be recorded. The AbbVie Medical Director must be notified if administration of any prohibited medication is reported during the study.

All allowable concomitant medications must be at a stable dose for at least 30 days prior to the subject's screening visit, and it is anticipated that no change in dose will be required during the study treatment period. All medications should remain at stable doses for the duration of the study unless a change in regimen is medically necessary. All concomitant medications, including any change in dose must be recorded with the reason for use, dates of administration, dosages and frequency in the eCRF.

Permitted medications include the following:

- Ramelteon, trazodone, amitriptyline and mirtazapine for sleep.
- Selective benzodiazepines and gamma-aminobutyric acid (GABA) agonists, zolpidem, zaleplon, eszopiclone, alprazolam, clonazepam and lorazepam for sleep and anxiety.
- Selective neuroleptics, clozapine or quetiapine for the treatment of psychotic symptoms.
- Selective serotonin reuptake inhibitors (SSRIs), serotonin-norepinephrine reuptake inhibitors (SNRIs), buspirone, mirtazapine or trazodone for anxiety or depression.
- Cholinesterase inhibitors (donepezil, rivastigmine, galantamine) or memantine for cognitive impairment.
- Medications for Parkinsonian symptoms (including levodopa/carbidopa, dopamine agonists, monoamine oxidase inhibitors, Catechol-O-Methyltransferase (COMT) inhibitors, or amantadine).

5.2.3.1 Prohibited Therapy

Unless approved by the Investigator in consultation with the Sponsor, subjects should not receive the following medications (not a comprehensive list) described in [Table 5](#).

Table 5. Prohibited Medications

Anticoagulants (Exclusionary for Lumbar Puncture)

Examples

Vitamin K antagonists

Dabigatran

Enoxaparin sodium

Rivaroxaban

Apixaban

Heparin

Neuroleptics*: Prohibited within 30 days prior to screening and throughout the duration of the study

Examples

Chlorpromazine

Fluphenazine

Loxapine

Perphenazine

Thioridazine

Thiothixene

Trifluoperazine

Haloperidol

Benzodiazepines/Gamma-Aminobutyric Acid (GABA) agonists*: Prohibited within 30 days prior to screening and throughout the duration of the study, such as:

Examples

Chlordiazepoxide

Diazepam

Midazolam

Flurazepam

Temazepam

Meprobamate

Triazolam

* Excluding the selected compounds mentioned in Section 5.2.3.

Additional recommendations are the following:

Drugs commonly known to cause excessive sedation, orthostatic hypotension or increased risk for falls should be avoided, if possible.

In general, dose changes or administration of additional medications with psychotropic effects (including opiates) on an as-needed (i.e., PRN) basis is prohibited. In the exceptional case, low doses of anxiolytic/hypnotic agents, antipsychotic or opiate containing medications are permitted in the interest of patient safety or emergent symptom control; however, ongoing use of PRN medications should be discussed with the AbbVie Medical Director. If a subject requires PRN use of a medication with psychotropic effects, subject efficacy scales must not be administered for at least 48 hours following the administration of the medication. Depending on the time of dose administration, the next study visit should be rescheduled to assure an interval of at least 48 hours between PRN medication administration and clinical or psychometric assessments. Each case of PRN medication administration must be documented with the reason for use, dates of administration, and dosages in the eCRF. Regularly scheduled medications administered to a subject on a daily basis should not be delayed, and administration times should not be altered due to cognitive assessments.

The AbbVie Medical Director should be contacted if there are any questions regarding concomitant and prior therapy(ies), or prohibited medications.

